Specific Aim 2: To compare patient- and provider-desired outcomes -- e.g., nicotine intake, carcinogen exposure, number of days abstinent, and side effects – among AA non-daily smokers receiving C versus C+NRT and, within the C+NRT group, examine the choice of NRT and use during the treatment period. Hypothesis: Participants randomized to C+NRT will demonstrate significantly greater reductions in nicotine intake and carcinogen exposure and significantly more days abstinent, while experiencing no differences in side effects as participants randomized to C. Analytic strategy: We will utilize linear mixed models to longitudinally (week 12 and 26) compare nicotine and carcinogen exposure between the two groups, then subsequently examine the effects of the covariates listed in the measurement table above using a best subsets selection method for both nicotine and carcinogen exposure independently. A generalized linear mixed model approach will be used to model days abstinent, controlling for number of days in study, to assess the effect of treatment on this endpoint and best subsets selection will be used to examine the effects of covariates on this endpoint. For each of these models, based upon the sample size, we anticipate that ten to twelve covariates could be included in a final model. We will compare the prevalence of any side effect as well as each specific side effect, from baseline to week 12, between the two groups using the chi-square test. If there is a global difference we will examine, within the NRT group, if type of NRT impacts the side effect profile. Within the NRT group we will descriptively summarize the number and percent of subjects who choose each type of NRT. Subsequently we will describe and descriptively compare the percent of subjects within each of these subgroups who use the NRT of choice during the treatment period (i.e., percent of patients within the patch, gum, and lozenge groups who used the medication).

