
These doses represent a starting point. To enhance the ability of our findings to be translated into practice, counselors will educate participants about the relationship between cpd and NRT dosing and empower them to tailor use to be consistent with their smoking patterns, intensity of withdrawal and craving, and level of side effects. Participants will be taught that, if the NRT dose is adequate, they may still have urges during the day, but most of the time they will not feel strong physical cravings or discomfort. They will also be educated about side effects that may indicate a nicotine overdose (nausea, vomiting, cramps, dizziness) and the need for a dose reduction (i.e., fewer pieces of gum/lozenge per day, reduction from 24 to 16 or 12 hours per day that the patch is worn), as well as symptoms of withdrawal (e.g., irritability, restlessness, anxiety) and strong physical craving that may indicate the need for a dose increase (i.e., more pieces of gum/lozenge per day, increase to longer wear or a higher dose patch). Counselors will probe for smoking level, use of NRT (days used, amount used per day), side effects, symptoms of withdrawal and craving, and general experiences with the

medication during the week 1, 4, 6, 8, and 10 sessions and will provide guidance, as necessary, to ensure that the medication is working optimally for each participant. The PI and study physician will provide oversight on questions and issues that arise related to side effects, dose reductions and/or increases.

Overview of Major Study Events

		Enroll./ Baseline					EOT	Final Follow- Up
		Wk 0*	Wk 1	Wk 4	Wk 8	Wk 10	Wk 12*	Wk 26*
Screening/ Assessments	X	X		X	X		X	X
Intervention								
Counseling		X	X	X	X	X		
Medication Dispensing (C+NRT only)		X (3 to 9- day trial period)	X	X	X		X	

*in person; all other visits are by telephone; EOT=end of treatment

Procedures and Methods

An overview of major study events is provided in the adjoining table.

Initial Screening.

The initial screen will review inclusion/exclusion criteria. Those eligible will be scheduled to complete final eligibility screening within 14 days. All ineligible smokers will be referred to local resources.

Final Screening and Enrollment (Wk 0). Final eligibility screening will be conducted in person and will consist of a pregnancy test on women of childbearing age and obtaining informed consent.

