Counseling Visits (Wks 0,1,4,8,10). Counseling sessions will be completed by phone at Wks 1,4, 8,10, and in person at Wk 0. The number of sessions is consistent with our previous studies where we have achieved visit completion rates of around 80%.^{45,55,56}

NRT Dispensing (Wks 0-1). Participants randomized to C+NRT will be given a trial supply of nicotine gum, patch, and lozenge and be instructed to try each for 3-days. After the 3 to 9-day trial period, they will select and be mailed a 4 week supply of the medication of their choice. They will receive refills of their selected medication at the Weeks 4 and 8 study visits.

Biological Sample Collection (Wk 0,12,26). Urine will be collected three times throughout the study for biochemical verification of cessation at Wk 12 and Wk 26, nicotine intake at Wks 0, 12, 26, and carcinogen exposure at Wks 0, 12, and 26. Additional details regarding each assay are provided in the Measures and Assessment Time Points table.

Retention. We have developed a system of reminders and compensation that have resulted in impressive retention rates in our previous clinical trials. Reminders. One week prior to each scheduled visit a reminder postcard noting the scheduled appointment date and time will be mailed to participants. In addition, participants will be called up to 6 times to remind them of their upcoming visit. A detailed tracking database, with an automated reminder system, will notify counselors of when to send postcards and complete reminder phone calls. Compensation. Participants will be given a \$40 electronically loaded gift card at Wks 0, 12 and a \$20 electronically loaded gift card at Wks 1, 4, 8, 10, 26 in appreciation for their time and participation.

Measures

Our selection of measures (see table) and the measurement time points have been driven by our patient and stakeholder advisory panels.

Measure and Assessment Time Points

Primary Scientific Outcome (Aim 1)

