Side effects. Participants will be asked about symptoms commonly associated with quitting smoking and/or NRT (i.e., difficulty concentrating, irritability, skin rash, mouth/throat irritation, nausea, sleep disturbance, heart burn) Time Points: Wks 4,8,12
Covariates (Aims 1, 2 & 3)
Demographics. Includes gender, age, income, education level, marital status, and use of alcohol Time Point: Wk 0
Smoking history. Includes type of cigarette (menthol, non-menthol), days smoked per month, number of cigarettes smoked per day on days smoked, length of time smoking at current non-daily rate, age of smoking initiation, time to first cigarette of the day (nicotine dependence), use of cigarettes only or cigarettes in combination with alternative forms of tobacco (ATP; e.g., cigars, cigarillos), presence of other smokers in the home, and home smoking restrictions Time Point: Wk 0
Treatment. Includes treatment assignment (C, C+NRT) and, for those randomized to C+NRT, their choice of nicotine gum, lozenge, or patch.

Clearly indicate which procedures, tests, visits, etc., are parts of usual standard therapy and which are performed solely for research purposes.

All tests, procedures, and visits are being performed solely for research purposes and are not billable to insurance companies.

Describe the fate of any body component (blood, CSF, bone marrow, etc.) used in the study, emphasizing confidentiality of labeling of the sample and the sample's destruction or storage.

Samples will be labeled only with a unique study identification number and only members of [name] and [name]'s team will have access to the samples. Samples will be disposed of one month after the final report is sent out to the Principal Investigator, unless participants agree to have their urine stored for future testing.

F. Risk/benefit assessment:

Physical risk

Risks for participating in the study are primarily those related to the use of NRT for participants randomized to the C+NRT arm. The safety of NRT has been demonstrated in hundreds of studies spanning over 30 years of research, including studies of patients who are very low level smokers and nonsmokers. To minimize any possible risk, we will exclude any patients with unstable heart disease (i.e., unstable angina or AMI in the past 4 weeks) per the medical contraindications for NRT.

Nevertheless, NRT, particularly in continuing smokers, can be associated with nausea, jitteriness,

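### The cumulative side-effect comparison takes no account of how many assessments each person completed, so unequal completion by arm could create or hide a difference

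*Combined protocol and SAP*

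**What the plan says.** Section II.C, Specific Aim 2, sets the comparison: "We will compare the prevalence of any side effect as well as each specific side effect, from baseline to week 12". The test is unadjusted: "from baseline to week 12, between the two groups using the chi-square test". The hypothesis is that C+NRT participants do better on the other outcomes "while experiencing no differences in side effects as participants randomized to C". A global difference leads to a further look at side effects by NRT product.

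The measures table in II.E lists seven symptoms and ends the entry "sleep disturbance, heart burn) Time Points: Wks 4,8,12". It lists no Week 0 reading and no recall period.

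On visits, II.E (Counseling Visits) says that in earlier studies "we have achieved visit completion rates of around 80" per cent, with no figure by arm. On NRT Dispensing it says "They will receive refills of their selected medication at the Weeks 4 and 8 study visits". The events table labels that row "Medication Dispensing (C+NRT only"). The Week 4 and 8 contacts are by telephone in both arms: "Counseling sessions will be completed by phone at Wks 1,4, 8,10, and in person at Wk 0".

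The general rules in II.C on loss to follow-up, including multiple imputation if loss differs by group, are written for smoking cessation. In Aim 2, days abstinent is adjusted for time in study. Side effects have no corresponding adjustment.

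**The concern.** The chance that a person reports a symptom at least once rises with the number of times that person is asked. A chi-square on a cumulative yes/no treats someone assessed once and someone assessed three times as equally observed. That does no harm to the comparison if completion is the same in both arms. If it is not, part of the observed difference is a difference in opportunity to report.

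There is a concrete reason to guard against this. Two of the three assessments coincide with a medication supply in one arm and not in the other. The plan already foresees differential loss for cessation, but not here.

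At stake are the Aim 2 statement on side effects, the trigger for the by-product analysis, and the contribution to the stated purpose (I.C) of judging whether NRT is safe in this population. A spurious excess would count against NRT. If completion were worse in C+NRT, a real excess could be masked.

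**Working it through.** **The plan's own figures.** The plan gives no figure for side effects. Its only design figures are power for Week 12 abstinence with 128 v 256: 95%, 87% and 71% for 10% v 25%, 22.5% and 20%. A two-sided 5% chi-square without continuity correction gives 95.7%, 87.6% and 71.7%. These agree, so the same test is used below.

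**Inputs from the documents.** 128 in C and 256 in C+NRT; three assessments; overall completion about 80%; type 1 error 5%.

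**Assumptions.** The true symptom rate is 25% per assessment in both arms. Completion is 70% v 85% or 75% v 82.5% (C v C+NRT). Both pairs average 80%: (128×70 + 256×85)/384 = 80 and (128×75 + 256×82.5)/384 = 80. The denominator is everyone randomized, and a missed assessment counts as no report.

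**Formula, independent visits.** With completion a at Weeks 4 and 8 and b at Week 12:

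P(any report) = 1 − (1 − 0.25a)² × (1 − 0.25b)

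For 70% v 85% at Weeks 4 and 8, with b = 80% in both arms:
- C: 1 − 0.825² × 0.80 = 45.6%
- C+NRT: 1 − 0.7875² × 0.80 = 50.4%
- Difference: +4.8 points with no true effect

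The false-positive rate comes from exact enumeration of the chi-square at these two proportions. The clustered rows give each person a random intercept (SD 1.5 on the logit scale) and keep the average rate at 25%.

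| Completion C v C+NRT | Gap applies at | Symptoms within person | Difference (points) | False positives |
|---|---|---|---|---|
| 80% v 80% | none | independent or clustered | 0 | about 5% |
| 75% v 82.5% | Wks 4, 8 | independent | +2.4 | 7.0% |
| 75% v 82.5% | Wks 4, 8 | clustered | +1.7 | 6.3% |
| 70% v 85% | Wks 4, 8 | independent | +4.8 | 14.0% |
| 70% v 85% | Wks 4, 8 | clustered | +3.4 | 10.0% |
| 75% v 82.5% | all three | independent | +3.6 | 9.9% |
| 75% v 82.5% | all three | clustered | +2.6 | 7.8% |
| 70% v 85% | all three | independent | +7.3 | 26% |
| 70% v 85% | all three | clustered | +5.2 | 17% |

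**Persistent symptoms.** Suppose a symptom lasts throughout and is reported at any completed assessment. With the 70% v 85% gap at Weeks 4 and 8, C gives 0.25 × (1 − 0.30² × 0.20) = 24.6% and C+NRT gives 0.25 × (1 − 0.15² × 0.20) = 24.9%. The false-positive rate is about 5%.

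**Reverse gap.** With 85% in C and 70% in C+NRT at Weeks 4 and 8, the same arithmetic gives 50.4% v 45.6%. That is −4.8 points, which could offset a real excess of similar size.

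**Denominator.** With a gap at all three visits (70% v 85%), restricting to people with at least one assessment gives 43.8/0.973 = 45.1% v 51.2/0.997 = 51.3%, and still about 21% false positives. Restricting to people with all three gives 1 − 0.75³ = 57.8% in both arms and removes the effect, provided missed visits are unrelated to symptoms. The result therefore depends on a choice that the plan does not state.

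**Visit-level comparison.** Comparing one visit among those assessed, with 80% v 90% complete and missed visits unrelated to symptoms, gives 4.9%, 5.0% and 5.2% false positives at symptom rates of 10%, 20% and 30%.

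**The case against.** The strongest reply is that nothing in the documents says completion will differ. Both arms have the same calls, the same reminders and the same $20 payment at Weeks 4 and 8, paid only for a completed visit. Those contacts are by telephone, so nobody travels to pick up a refill, and no text makes a refill conditional on answering the symptom questions. The NRT paragraph in II.E speaks of a 12-week supply after the trial period, NRT Dispensing describes a 4-week supply with refills, and the events table also marks dispensing at Week 12. These passages need reconciling, and the strength of any refill incentive depends on the outcome. With equal completion there is no bias.

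This stands. A reader might infer that C+NRT will attend better and that a false excess is therefore to be expected. The documents do not support that; they support only an unprotected comparison.

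A reader might also take 26% as the size of the problem. That figure needs a 15-point gap at all three visits and independent symptoms, whereas NRT Dispensing names only Weeks 4 and 8 for refills.

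It is also fair that one yes/no per person is an inference, since coding, denominator and recall period are undefined. A question that reached back over missed intervals would shrink the effect. Finally, whether a person had the side effect by Week 12 is a legitimate patient-facing question, so replacing the cumulative measure outright is not warranted.

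**Conclusion.** The concern holds as a gap in the analysis plan. On its most natural reading, the planned test cannot separate a true difference in side effects from a difference in the number of completed assessments, and the protection written for cessation does not extend to this outcome.

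For a gap confined to the refill visits the inflation is moderate: about 10-14% false positives for a 15-point gap and 6-7% for a 7.5-point gap, against a nominal 5%. It disappears with equal completion and nearly so with persistent symptoms. It reaches 17-26% only if the 15-point gap extends to Week 12. All of this rests on the assumed 25% symptom rate and assumed completion by arm. The direction is unknown.

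It would also be too strong to say that a visit-level model always holds 5%. It does so only under its own missing-data condition, set out with the fix. The outcome is secondary and the by-product analysis is a follow-on, but the comparison feeds a safety conclusion and the remedy is cheap.

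**What to change.** In II.C, Specific Aim 2:

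1. Define the side-effect variable, its recall period, its denominator and the handling of a missed assessment. Keep the cumulative percentages and chi-square on that definition.
2. Add a logistic GEE or mixed model of each symptom, and of any symptom, at each completed assessment (Weeks 4, 8 and 12), with arm and visit as terms. Report per-visit prevalence by arm with 95% confidence intervals.
3. Report completion of the side-effect assessment by arm and visit beside these results.
4. Treat the arms as differing, and start the by-product follow-on, only where the difference also appears in the visit-level analysis. Rest any statement of no difference on the visit-level estimates and intervals as well.

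The cost is a few sentences and some programming. The data are already collected, and GEE and mixed models are already planned for other outcomes. The limit is that the GEE needs missed assessments to be unrelated to symptoms given arm and visit, and the mixed model needs this given the observed reports as well. If people with side effects stop answering calls for reasons that those terms do not capture, neither analysis corrects it; completion by arm would at least show where to look.

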University of Kansas Medical Center
RESEARCH PROTOCOL INVOLVING HUMAN SUBJECTS
TEMPLATE WITH GUIDANCE

Version date: 5/24/2018

Principal Investigator: [name]

Study Title: Informing Tobacco Treatment Guidelines for African American Non-Daily Smokers

Co- Investigator(s): [name], [name], [name]

(NOTE: not all sections of this template will apply to all projects. "N/A" is an acceptable response.)

I. PURPOSE, BACKGROUND AND RATIONALE

A. Aim and Hypotheses

Non-daily smokers, i.e., those who smoke on some but not all days, represent a substantial and growing proportion of racial/ethnic minority smokers. 1 out of 4 African Americans (AA) are non-daily smokers. AAs experience disproportionately greater smoking attributable morbidity and mortality at lower levels of smoking and AA non-daily smokers have strikingly higher levels of nicotine and the potent carcinogen, NNAL, than White and Hispanic non-daily smokers, despite a comparable level of smoking. To date, however, no evidence-based treatment guidelines exist for non-daily smokers, leaving health care providers wondering how to treat this high risk and growing subgroup, and **no** fully powered studies have been conducted to explore treatment options for non-daily smokers.

The specific aims of our study are to:

- 1) **Compare abstinence rates among AA non-daily smokers receiving either smoking cessation counseling (C) or smoking cessation counseling in combination with NRT (C+NRT).** Hypotheses: Participants randomized to C+NRT will have significantly higher biochemically verified smoking abstinence than participants randomized to C at 12 weeks end of treatment (primary outcome) and at 26 week follow-up.
- 2) **To compare patient- and provider-desired outcomes -- e.g., nicotine intake, carcinogen exposure, number of days abstinent, and side effects -- among AA non-daily smokers receiving C versus C+NRT and, within the C+NRT group, examine choice and use of NRT during the treatment period.** Hypothesis: Participants randomized to C+NRT will demonstrate significantly greater reductions in nicotine intake and carcinogen exposure and significantly more days abstinent, while experiencing no differences in side effects as participants randomized to C.

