C. Sample size, statistical methods, and power calculation

384 AA non-daily smokers will be randomized. We will use 2:1 randomization; for every patient randomized to C, two will be randomized to C+NRT (see Figure). Randomization will be determined by computer-generated random numbers generated by [name]. Randomization assignments will be placed in sealed envelopes by a member of [name] team with sequential study ID numbers. After baseline data collection has been completed, the research assistant will select the sequential study ID number from the sealed envelope to determine the randomization assignment.

The maximum number of participants enrolled in C will be 128 and the maximum number enrolled in C+NRT will be 256. Our sample size is based on our primary outcome, biochemically confirmed point-prevalence abstinence at Week 12 using an intent-to-treat approach. Based on treatment studies with AA light smokers who have received tobacco treatment guideline-based counseling and no pharmacotherapy, we expect a 10% point prevalence abstinence rate in the C group and a 20-25% point prevalence abstinence rate in the C+NRT group based on recent meta-analyses and studies examining the effectiveness of these medications in AA light smokers.^{11,28,45,46} Using the chi-square test, along with the assumptions above, 256 participants in the C+NRT group and 128 participants in the C group (n=384), we will have 95% power to detect an increase from 10% to 25% in cessation at Week 12 between C and C+NRT, 87% power to detect a and increase from 10% to 22.5%, and 71% power to detect an increase from 10% to 20% with a type 1 error rate of 5%.

Analysis Plan for Each Aim

All primary analyses on smoking cessation will be conducted using intent-to-treat and will code those lost to follow-up as smokers. Subsequently we will evaluate the missing data pattern. If there is a differential loss based upon group, multiple imputation techniques will also be used.

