Specific Aim 1: To compare abstinence rates among AA non-daily smokers receiving either smoking cessation counseling (C) or smoking cessation counseling in combination with NRT (C+NRT). Hypothesis: Participants randomized to C+NRT will have significantly higher biochemically verified smoking abstinence than participants randomized to C at 12 weeks end of treatment (primary outcome) and at 26 week follow-up. Analytic strategy: The chi-square test will be used to compare the verified abstinence rates at Week 12 (primary cessation endpoint) and Week 26 (secondary cessation endpoint) between C and C+NRT. For our primary comparison, those lost to follow-up will be considered as smokers. Assuming the expected treatment effect, we will descriptively examine the cessation rate within the C+NRT group by choice of NRT. A statistical comparison will not be conducted as we do not know a priori who will choose what and the choice will not be random. We also will look at completers only and will utilize multiple imputation techniques to ensure valid comparisons between the two groups if the loss to follow-up is not random. Secondly, we will utilize Generalize Estimating Equation methodology to longitudinally compare verified abstinence. We will then examine the effects

of the covariates and patient and provider outcomes listed in the measurement table above on this endpoint by utilizing best subsets selection techniques. Our goal is to identify a final model utilizing the smallest subset of covariates that describes cessation over the length of the study. Given the sample size and expected cessation rate, we anticipate a model that contains at most six covariates. We expect no difference in the distribution of demographic and smoking history covariates between groups and we will not statistically compare those as per CONSORT recommendations for randomized clinical trials. Within the NRT treatment group, we will examine the effect of NRT adherence over the first 12 weeks on verified cessation using logistic regression.

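### Aim 2 hypothesises no difference in side effects, but the plan only tests for a difference, and it looks at side effects by product only after a global difference is found

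*Combined protocol and SAP*

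**What the plan says.** Section I.A (Aim 2) and section II.C (Specific Aim 2) both state, as part of a labelled hypothesis, that C+NRT participants will improve on exposure and days abstinent "while experiencing no differences in side effects as participants randomized to C".

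The analysis for this in II.C covers "any side effect as well as each specific side effect, from baseline to week 12, between the two groups using the chi-square test". It is followed by a conditional step: "If there is a global difference we will examine, within the NRT group, if type of NRT impacts the side effect profile". The term global difference is not defined.

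For cessation by product, Specific Aim 1 takes a different line. It says "we will descriptively examine the cessation rate within the C+NRT group by choice of NRT", with no statistical comparison, because "we do not know a priori who will choose what and the choice will not be random". In Specific Aim 2, choice and use of each product are also described without any gate.

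The Measures table lists seven symptoms, asked about at weeks 4, 8 and 12. The loss-to-follow-up rule in II.C covers cessation only ("All primary analyses on smoking cessation will be conducted using intent-to-treat and will code those lost to follow-up as smokers"), so the denominator for side effects is not stated.

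**The concern.** **Hypothesis and test do not match.** A chi-square test can produce evidence against equality. It cannot produce evidence for it. II.C gives no interval, no margin and no rule for reading a non-significant result. The plan does not say that p>0.05 will be read as no difference, but it offers nothing else that could support the hypothesis. Section I.C says the trial will establish whether NRT is safe in this population, so the side-effect comparison is likely to be quoted.

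**The gate can hide a product effect.** An effect confined to users of one product is diluted when all C+NRT participants are pooled. It is diluted again inside an any-side-effect composite, if many people report some symptom anyway. The listed symptoms include ones the protocol itself attributes to quitting, and both arms are trying to quit, so a common composite is plausible. Patch, gum and lozenge users are a natural unit for reporting side effects, yet the plan may never look at them separately.

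**Working it through.** **Inputs.** From section II.C: 128 in C, 256 in C+NRT, 5% type 1 error, chi-square test. Side-effect rates, product shares and margins are not in the documents; every such value below is an assumption.

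**Method.** z = (p̂₂ − p̂₁) / √[p̄(1−p̄)(1/n₁ + 1/n₂)], where p̄ is the pooled proportion, with no continuity correction. The result is significant if |z| > 1.96. Power is the sum of the exact binomial probabilities of all outcomes that are significant.

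**1. The plan's own power figures.** II.C states 95%, 87% and 71% for abstinence of 25%, 22.5% and 20% against 10%. The exact method gives 96.0%, 88.3% and 72.9%. The pooled normal approximation gives 95.7%, 87.6% and 71.7%. Taking 10% versus 20% as the example:

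- p̄ = (128×0.10 + 256×0.20)/384 = 0.1667
- null SE = √(0.1667×0.8333×0.01172) = 0.0403
- alternative SE = √(0.09/128 + 0.16/256) = 0.0364
- power = Φ[(0.10 − 1.96×0.0403)/0.0364] ≈ Φ(0.574) ≈ 0.717

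The plan's figures reproduce, so the method is a fair one to carry over to side effects.

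**2. Power of the planned test for a true excess in one symptom.** The second column takes 80% of each arm as analysed. That is an assumption, prompted by the visit completion of about 80% that the protocol cites from earlier studies.

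| C vs C+NRT | 128 vs 256 | 102 vs 205 |
|---|---|---|
| 5% vs 10% | 38% | 30% |
| 10% vs 15% | 27% | 22% |
| 20% vs 25% | 19% | 16% |
| 5% vs 15% | 87% | 78% |
| 10% vs 20% | 73% | 62% |
| 20% vs 30% | 56% | 47% |
| 50% vs 60% | 47% | 39% |

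Ten-point rises in uncommon symptoms would usually be seen. Five-point rises, and ten-point rises in common symptoms, would often be missed.

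**3. What a non-significant result can contain.** Take 26/128 (20.3%) versus 72/256 (28.1%).

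- Risk difference = 0.281 − 0.203 = 0.078
- Test: p̄ = 98/384 = 0.255, SE = 0.0472, z = 1.66, p = 0.098
- Wald SE = √(0.203×0.797/128 + 0.281×0.719/256) = 0.0453
- 95% CI = 0.078 ± 1.96×0.0453 = −1.1 to +16.7 points

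The test is non-significant, and an excess of 16 points is not excluded.

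**4. The gate.** Suppose one product raises one symptom by 15 points among its users, who form a share s of C+NRT.

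(a) If the gate is that symptom's own test, the C+NRT rate is b + 0.15s for background b. With s = 1/3 the arm-level rise is 5 points. Power is 70%, 38%, 27% and 19% at b = 1%, 5%, 10% and 20%.

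(b) If the gate is the any-side-effect test with rate c in C, the C+NRT rate is c + 0.15s when every extra case is new to the composite. It is c + 0.15(1−c)s when extra cases overlap independently with other symptoms.

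| Composite rate in C | s = 1/3, all new | s = 1/3, overlap | s = 1/2, all new | s = 1/2, overlap |
|---|---|---|---|---|
| 30% | 16% | 10% | 30% | 17% |
| 50% | 15% | 7% | 29% | 10% |
| 70% | 19% | 6% | 36% | 8% |

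**The case against.** **The hypothesis may be an informal expectation.** The wording for efficacy speaks of significance and the wording for side effects does not. A chi-square test can refute the expectation, and the arm rates it compares are enough to compute a risk difference later. This is fair as far as it goes. But the statement sits under the heading of a hypothesis, and nothing in II.C commits to reporting a difference with an interval.

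**Global difference is undefined.** It could mean any arm-level difference, including one in a single symptom, and not only the composite. That ambiguity is real. The composite is the more natural reading, because the preceding sentence sets any side effect against each specific one. Both readings are shown above. Under the symptom-level reading the gate works better, but power is still only 19% to 38% at backgrounds of 5% to 20%.

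**The scenarios could be kinder.** If an effect is shared by gum and lozenge and two thirds choose one of them (an assumption), a 15-point rise becomes 10 points at arm level. Symptom-level power is then 99%, 87%, 73% and 56% at backgrounds of 1%, 5%, 10% and 20%. So the gate is not always weak. It is weak for effects limited to one product, which a by-product analysis exists to find.

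**Symptoms could fall under NRT.** Some listed symptoms reflect withdrawal, so a two-sided equivalence rule would penalise a benefit. This stands, and it is a reason to prefer estimation or a one-sided claim.

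**The 80% figure is indirect.** It is visit completion, and side effects are asked at three visits, so more than 80% may contribute. Both columns are therefore given.

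**Missing text.** Part of the safety text before the adverse-event paragraphs was not available to us. The point concerns the analysis plan in II.C.

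**Conclusion.** The concern holds. As written, II.C contains no analysis that could support the side-effect hypothesis, and its gate can leave a product-specific effect unexamined.

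The mismatch needs no assumed rate; its size does. Over the assumed rates, the planned test misses a 10-point excess between 13% of the time (from 5%) and 53% of the time (from 50%) with all 384 analysed. The gate fails to open for a 15-point effect in one third of C+NRT between 81% and 94% of the time on the composite reading. On the symptom-level reading it fails between 30% and 81% of the time, depending on background.

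The plan should be changed on this point, but it concerns one secondary outcome. The primary endpoint, the sample size and individual adverse-event monitoring are unaffected.

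**What to change.** **Between-arm comparison.** For each of the seven symptoms and the composite, report the number analysed per arm and the risk difference with its 95% interval. State that p>0.05 will not be read as no difference. Then choose one of two routes:

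- Reword the side-effect part of Aim 2 as estimation.
- Keep a claim, with a margin the trial team fixes in advance. No worse requires the upper limit below the margin. No difference requires both limits within it. A claim across all seven symptoms and the composite requires all eight to pass.

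**By product.** Delete the global-difference condition and always tabulate side effects by chosen product, without tests between products. The plan's own reason for not testing cessation by product, non-random choice, applies here too.

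**Cost.** Only analysis-plan wording changes; no new data are needed. By-product cells will be small. The margin route may not deliver the claim. With truly equal arms and an illustrative 10-point margin, the chance of success per endpoint, using 95% limits, is:

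| Prevalence | No worse, 128 vs 256 | No worse, 102 vs 205 | No difference, 128 vs 256 | No difference, 102 vs 205 |
|---|---|---|---|---|
| 5% | >99% | 98% | 97% | 92% |
| 10% | 89% | 82% | 74% | 58% |
| 20% | 64% | 54% | 28% | 9% |
| 50% | 46% | 37% | about 0% | about 0% |

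With 90% limits, as in two one-sided 5% tests, the no-difference chances at 128 versus 256 are 98%, 85%, 50% and 14%. The joint chance over eight endpoints cannot exceed the lowest single one. Estimation wording avoids this cost.
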